In the prior cycle of this Program Project, a number of findings from diffusion tensor imaging and fluid biomarkers associated with inflammation were identified as predisposing to delirium. However, it is not clear whether those biomarkers might have been associated with preclinical AD pathology, vulnerable aging, or other known pathologies. Using modern magnetic resonance imaging (MRI) techniques, we have identified an "AD-Signature" of cortical atrophy and hippocampal hyperactivation as biomarkers of prodromal or preclinical AD. In addition, measures of changes in the brain that are associated with age-related cognitive decline in the absence of neurodegenerative or cerebrovascular disease can be detected as a "Vulnerable Aging-Signature" of cortical atrophy and reduced frontoparietal functional connectivity. Therefore, the overarching goal of Project 3 is to examine whether neuroimaging biomarkers of preclinical AD or vulnerable aging are predictive of delirium, delirium severity, and complicated delirium (i.e., delirium with LTCD), and to link these neuroimaging biomarkers to molecular biomarkers of pathology measured in the cerebrospinal fluid (CSF) and plasma. The Specific Aims are: 1) to determine in people with evidence of preclinical AD (i.e. patients with abnormal CSF AD biomarker levels of tau and beta-amyloid or classified as amyloid-positive in PET imaging) whether ADrelated brain atrophy or network dysfunction are associated with delirium, delirium severity, or LTCD; 2) to determine in people without evidence of preclinical AD (i.e. patients with normal AD biomarkers) whether vulnerable aging-related brain atrophy or network dysfunction are associated with delirium. delirium severity, or LTCD; and 3) to investigate whether longitudinal cortical atrophy (measured preoperatively and one year after surgery) due to preclinical AD or vulnerable aging is associated with postoperative LTCD or complicated delirium. To test these hypotheses, we will leverage the existing SAGES I cohort (N=560 total, n=126 with longitudinal MRI), augmented by new CSF (or PET) and MRI data collected in 148 SAGES I probability sampled patients (SAGES I SELECT) (74 with delirium, 74 without) about four years after their surgery, and a new SAGES II cohort (N=460), of which 180 patients will have both CSF (or PET) and MRI collected pre-operatively. The long-term objective of this Project is to improve the pathophysiological understanding of brain vulnerability to delirium in order to inform prevention strategies and, ultimately, pathophysiological-based treatments.

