Aim 1: Determine in people with evidence of preclinical AD whether AD-related brain atrophy or network dysfunction are associated with delirium, delirium severity, or LTCD. Power Analysis: For H1a, the SAGES II MRI sample has 180 subjects. We expect 32% to have abnormal CSF AD biomarkers⁶⁵ (n=57). Based on published rates⁶⁶, we expect 36% of the AD biomarker positive sample to develop delirium. From our previous studies, the mean of AD-signature cortical thickness is 2.49mm (SD 0.14). We assume this distribution for the non-delirium patients. A conservative effect size of 5%

decrease in cortical thickness for the delirium patients yields a mean of 2.37mm. With type-I error of 0.05, we obtained a power estimate of 0.87. For H1b, the SAGES I SELECT cohort has 148 patients. With 34% assumed to have abnormal CSF AD biomarkers, this yields 44 subjects. We assume that for those without delirium and no LTCD, cortical thickness has the same distribution as stated above and that those with both delirium and LTCD would have even greater atrophy than delirium alone; thus a slightly increased but still conservative threshold of 7% decrease yields 2.37mm. The power estimate is 0.97 given this sample and relative difference of the two cortical thickness means. For H1c, the combined sample size would be 48+44=92. The estimated pairwise Spearman correlation coefficient among the MRI and CSF biomarker variables would be statistically significantly detected at the level of correlation equal to at least 0.4 from the null estimate of 0.1, and power of 0.87.

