Aim 1 Analysis: For this aim, we will restrict the sample to only those subjects who have abnormal CSF or PET AD biomarkers. For H1a, we will use 2 GLM models, one for delirium incidence (log link), and one for delirium severity (identity link). The independent variables for these models are the variables from domain 2 (AD cortical thickness, memory network connectivity, hippocampal hyperactivity). Included in these GLM models are also potential confounders of demographic and baseline clinical variables. The estimated coefficients and 95% confidence intervals will allow us to assess the independent adjusted effects of this domain on delirium outcomes in this cohort of patients with abnormal preclinical AD biomarkers. We will estimate goodness-of-fit of these models by checking model residuals, estimates of the area under the ROC curve, and adjusted model R² values. For H1b, the four variables from domain 2 will be treated as independent variables in a Generalized Linear Mixed model with identity link, and the dependent variables in this model will be the longitudinal GCP values. In this model, delirium status, and the interaction between GCP and delirium status are also included. This model allows the estimation of the association (slope) between domain 2 variables, and GCP-based long term cognitive decline modified by delirium status. For H1c, we will report the correlation matrix using the nonparametric Spearman correlation coefficients for pairwise correlation among the variables of domains 2 and 4 (A β , p-tau, t-tau, NFL).

Aim 2 Analysis and Statistical Power: For this aim, we will restrict the sample to only those subjects who have normal CSF or PET AD biomarkers. The statistical approach for H2a and H2b is the same as described for Aim 1 but the independent variables for these models are the variables from domain 4 (vulnerable aging cortical thickness, frontoparietal functional and structural connectivity). For H2c, we will report the correlation matrix using the nonparametric Spearman correlation coefficients for pairwise correlation among domain 4 variables and the inflammatory biomarker variables found in Project 2.

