Aim 3 Analysis and Statistical Power: We will estimate the association between cortical atrophy due to either preclinical AD or vulnerable aging and LTCD (i.e. longitudinally measured GCP). We will treat atrophy as a binary outcome variable in the multivariable GLM model with log link, and repeated GCP measurements as independent variables. We will estimate the slope of GCP at each follow-up time point. In the event that we have high correlation among the GCP measurements, we will make use of the distributed lag model to mitigate the collinearity problem. For H3b, we will add to this GLM model from H3a, delirium status (binary), and the interaction between GCP and delirium status, and will obtain GCP slope conditioning on delirium status.

Project 4

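### Project 3, H1b and H2b: the outcome, GCP, is also entered as a predictor through a GCP-by-delirium term, and the listed terms cannot give decline modified by delirium

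*Protocol*

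**What the plan says.** Protocol B.2.3, Project 3, Aim 1 Analysis restricts the sample to patients with abnormal AD biomarkers. For H1b it specifies a generalized linear mixed model with identity link.

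- Exposures: "the four variables from domain 2 will be treated as independent variables".
- Outcome: "the dependent variables in this model will be the longitudinal GCP values".
- Further terms: "In this model, delirium status, and the interaction between GCP and delirium status are also included".
- Stated target: "This model allows the estimation of the association (slope) between domain 2 variables, and GCP-based long term cognitive decline modified by delirium status".

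Aim 2 works in patients with normal biomarkers and takes over the model with other imaging variables: "The statistical approach for H2a and H2b is the same as described for Aim 1".

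The power section (B.1.3, Project 3) places H1b in the nested SAGES I cohort: "For H1b, the SAGES I SELECT cohort has 148 patients". A.2.3 gives that cohort's make-up as "74 with delirium, 74 without". The power section counts 44 biomarker-abnormal patients for H1b and 88 biomarker-normal patients for H2b.

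**The concern.** A variable cannot serve as the outcome and, multiplied by a group indicator, as a predictor in the same regression. GCP times delirium is zero in patients without delirium and is the GCP score itself in patients with delirium. The model can therefore reproduce the delirious patients' outcomes almost exactly without using the imaging markers.

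The question is also about decline, and about whether delirium changes the link between imaging and decline. That needs an imaging-by-time term, and an imaging-by-delirium-by-time term for the modification. The paragraph names neither. An analyst who followed it would report an imaging coefficient that is pulled toward zero and describes GCP level rather than change. A null result on the long-term-decline hypotheses of Aims 1 and 2 could not be interpreted.

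**Working it through.** **Inputs.** The outcome, predictors and cohort are as listed above. Two quantities are not in the protocol and are assumed here:
- p, the delirium share within the biomarker-restricted subset: 0.36 to 0.60. The whole nested cohort is 74:74, so 0.50. The only biomarker-positive delirium rate in B.1.3, Project 3 is 36%, and it is for SAGES II.
- rho, the within-group correlation of imaging marker and GCP: 0.1 to 0.5.

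**1. The plan's own figures.** B.1.3 states power 0.97 for H1b. A 7% decrease from 2.49 mm is 0.174 mm; over SD 0.14 that is 1.245 SD. Two-sided at 0.05 with 44 patients, power is 0.98 for a 22/22 split and 0.97 for 16/28. For H2b, 7% of 1.94 mm is 0.136 mm with SD 0.18; at 44/44 the power is 0.94, as stated. Both figures reproduce, but as two-group comparisons of cortical thickness. They say nothing about the mixed model. (The mean printed for H1b, 2.37 mm, is the 5% figure; 7% gives 2.32 mm.)

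**2. Algebra.** Fit Y = a + bX + cD + g(Y x D), where Y is GCP, X the imaging marker and D delirium. Let beta be the true within-group coefficient of X. With X and Y centred within group, least squares minimises

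(1-p) E(Y - bX)^2 + p E((1-g)Y - bX)^2.

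- Over g: 1-g = b cov(X,Y)/var(Y). The second part becomes p b^2 var(X)(1-rho^2).
- Over b: (1-p)(b - beta) + p b (1-rho^2) = 0, so **b = beta (1-p)/(1 - p rho^2)**.

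At p = 0.50 and rho = 0.3: 0.50/(1 - 0.50 x 0.09) = 0.50/0.955 = 0.52.

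| Share of imaging coefficient retained | rho 0.1 | rho 0.3 | rho 0.5 |
|---|---|---|---|
| p = 0.36 | 0.64 | 0.66 | 0.70 |
| p = 0.50 | 0.50 | 0.52 | 0.57 |
| p = 0.60 | 0.40 | 0.42 | 0.47 |

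**3. Check with mixed models.** Data were simulated with six visits, a random intercept and a true imaging coefficient of 0.40. With 400 patients and p = 0.50, the estimate is 0.40 without the GCP-by-delirium term and 0.21 with it (ratio 0.52). At p = 0.36 and 0.60 the ratios are 0.65 and 0.41. With 44 patients they are 0.62, 0.58 and 0.45 at p = 0.36, 0.50 and 0.60. The GCP-by-delirium coefficient is 0.98 to 0.99 throughout.

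**4. Level against decline.** Two situations were simulated (400 patients, p = 0.50): imaging affects GCP level only, or GCP slope only. With no time term, the imaging coefficient is 0.39 and 0.40 respectively without GCP x delirium, and 0.19 and 0.20 with it. The two situations cannot be told apart. With imaging, time and delirium fully interacted, imaging x time is 0.01 when the true slope effect is 0, and 0.80 when it is 0.80.

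**5. Adding time but keeping the term.** In simulations with 148 patients and 8 visits, imaging x time was -0.052 with GCP x delirium kept and -0.100 without it. When imaging affected slope only in patients with delirium (true effect -0.20; 60 data sets, so illustrative), imaging x time was -0.003 with the term kept. A model with imaging x delirium x time and a random slope gave -0.205.

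**The case against.** **It is probably a slip.** In Aim 3 (H3b) the same GCP-by-delirium interaction is legitimate, because GCP is a predictor there, and the phrase may have been carried over. The sentence that follows it in H1b shows the intended target, and Project 1 shows that the team writes GCP trajectory models correctly. This is likely. It means no biased result has been shown to follow, only that the printed model is wrong. It does not make the point a matter for a later analysis plan: such a plan would have to contradict this text, not fill a gap in it.

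**Time may be implied.** The delirium terms are introduced as additions, so the list need not be complete. Table 6 names repeated-measures and mixed-effects models for Project 3, and B.2.1 promises control for retest effects. This stands in part. A reader might infer that the plan has no time term at all, but silence in a short paragraph does not establish that. What can be said is that the listed terms do not give the target, and that adding time alone does not repair the model (step 5).

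**Halving is not a fixed figure.** A reader might take one half as the size of the bias. It follows from a 50:50 split, which the protocol gives for the whole nested cohort and not for the biomarker-restricted subsets. Only the range is supported.

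**Aim 3.** A reader might extend the criticism there, since the plan says: "We will treat atrophy as a binary outcome variable in the multivariable GLM model with log link, and repeated GCP measurements as independent variables". The documents do not support this. GCP is properly a predictor in that model, a distributed lag model is provided for collinearity, binary atrophy matches the power basis in B.1.3, and the direction of regression is a choice when the aim is association.

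**Conclusion.** The point holds for H1b and, by inheritance, H2b. The protocol positively states a term that makes the outcome its own predictor. Fitted as written, the imaging coefficient keeps about 0.4 to 0.7 of its value, and about 0.5 at an even delirium split. This rests on assumed delirium shares of 36% to 60% and rho of 0.1 to 0.5. The terms named cannot deliver an association with long-term decline modified by delirium, whatever the shrinkage. The stated power figures neither support nor rescue the model, because they belong to a different comparison. The finding does not reach Aim 3.

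**What to change.** In B.2.3, Project 3, delete GCP x delirium from H1b and so from H2b. Use the piecewise GCP mixed model set out for Project 1 H1b, which Project 1 Aim 2 already applies to the nested SAGES I cohort. Its terms should be time, imaging marker, delirium, imaging x long-term time, delirium x long-term time, and imaging x delirium x long-term time for the modification.

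Enter the imaging markers one at a time, or name one primary marker, because only about 44 (H1b) and 88 (H2b) patients are available. In the same edit, settle how many domain 2 variables there are (H1a lists three, H1b refers to four) and the use of domain 4 for both fluid biomarkers and aging imaging variables.

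The cost is a rewording of the Aim 1 and Aim 2 analysis paragraphs, with no change to data or sample. The drawback is that the three-way term will be imprecise at these sizes. The text should say so, and B.1.3 offers no power figure for it.

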Aim 3. Investigate whether cortical atrophy due to preclinical AD or vulnerable aging is associated with postoperative LTCD or delirium with LTCD. Power Analysis: For H3a, using estimates from prior work,⁶⁷ the estimated mean prevalence of cortical atrophy of either preclinical AD or aging is 19.3%. We assume this estimate for the no delirium group, and a relative risk of 2.5 of having cortical atrophy for the delirium group. Of the 126 subjects, 22% (n=28) subjects had delirium, and 98 did not. Given these estimates, the power is 0.82. For H3b, among those with delirium and LTCD relative to those with no delirium, and no LTCD, we assume that the conditional probability of having LTCD given that one has delirium is 70%, and the conditional probability of having LTCD given that one does not have delirium is 20%. Given these estimates, the joint frequency distribution is N=20 for those with both conditions of delirium and LTCD, and N=78 for those with neither condition. The expected relative risk would be higher in this comparison than 2.5 in H3a. With a power of 0.81, and the given sample size of 126, we could detect a statistically significant relative risk of at least 2.75 at type-I error of 0.05.

Project 4

Aim 1a: Mount a Modified Delphi Process Involving Delirium Experts to Identify Predictors of Delirium and Cognitive Decline Following Delirium (Complicated Delirium) for Early Identification. Statistical Power Considerations: N/A

Aim 1b. Operationalize and Evaluate the Accuracy of the Predictors for Complicated Delirium. Statistical Power Considerations. Our pilot data suggest we might expect a correlation between model-implied cognitive slope and observed cognitive slope of about r = .54. With 375 patients in the model development sample and 185 in the model testing sample, we used Monte Carlo procedures to determine that we will have an 80% probability of obtaining a correlation between .48 and .60 in both the model development and model testing samples. Therefore, we believe this aim is adequately powered to generate a reasonable probability of identifying a replicable model.

Aim 2a: Identify and Cross-Validate Predictors of Complicated Delirium. Statistical Power

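### Project 3 Aim 3 reduces one-year cortical atrophy to yes/no with no stated cut-point or reason, which discards information in a fixed sample of 126

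*Protocol*

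**What the plan says.** Protocol section A.2.3 (Project 3) describes the Aim 3 measure as "longitudinal cortical atrophy (measured preoperatively and one year after surgery"), drawing on the existing SAGES I cohort with "n=126 with longitudinal MRI".

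Section B.2.3, Project 3, Aim 3 fixes the analysis: "We will treat atrophy as a binary outcome variable in the multivariable GLM model with log link, and repeated GCP measurements as independent variables". For H3b, delirium status and its interaction with GCP (General Cognitive Performance) are added.

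Section B.1.3, Project 3, Aim 3 powers the aim in the same binary form. It says that "the estimated mean prevalence of cortical atrophy of either preclinical AD or aging is 19.3" per cent, applies this to the no-delirium group, and assumes "a relative risk of 2.5 of having cortical atrophy for the delirium group". The group sizes are given as "Of the 126 subjects, 22% (n=28) subjects had delirium, and 98 did not", and the result as "Given these estimates, the power is 0.82". For H3b it compares 20 participants with delirium and long-term cognitive decline (LTCD) against 78 with neither, and gives a detectable relative risk of 2.75 at power 0.81.

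Elsewhere in the project, thickness stays in mm. For Aim 1, section B.1.3 says that "the mean of AD-signature cortical thickness is 2.49mm (SD 0.14"), and Aim 2 uses 1.94 mm (SD 0.18). Both aims are powered on a difference in mean thickness.

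**The concern.** A change in cortical thickness between two scans is a continuous quantity. Cutting it into yes/no treats a participant just past the cut like one with severe thinning, and a participant just short of it like one with none. The protocol commits to this in both the analysis and the power text, without saying where the cut lies or why one is needed.

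The sample consists of scans already collected, so recruitment cannot replace the lost information. At stake is the chance of detecting a real association of thinning with delirium or cognitive decline.

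**Working it through.** **Inputs.** From B.1.3, Project 3, Aim 3: reference rate 0.193; H3a relative risk 2.5, 28 v 98; H3b relative risk 2.75, 20 v 78. From B.1: two-sided alpha 0.05.

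**1. The plan's own figures.**
- H3a: 2.5 × 0.193 = 0.4825. Fisher's exact test, enumerated over all outcomes for 28 v 98, gives power 0.822 (stated 0.82).
- H3b: 2.75 × 0.193 = 0.53075. For 20 v 78 it gives 0.815 (stated 0.81).

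Both reproduce.

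**2. The same contrasts under the planned model.** B.2.3 names a log-link GLM, tested by likelihood ratio or by Wald on the log relative risk. By enumeration, H3a power is 0.848 and 0.873; H3b power is 0.833 and 0.866.

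**3. The same effects on a continuous scale.** Assume atrophy is a cut of one change score with the same distribution shape and SD in both groups.
- Normal threshold, H3a: d = z(0.4825) − z(0.193) = −0.044 + 0.867 = 0.823. Noncentrality = 0.823 × √(28 × 98 / 126) = 0.823 × 4.667 = 3.84. Two-sided t-test power is 0.968.
- Logistic conversion, H3a: odds ratio = (0.4825/0.5175) / (0.193/0.807) = 3.90; d = ln(3.90) × √3/π = 0.750. Power is 0.935.
- H3b by the same steps: d = 0.944 or 0.857, power 0.962 or 0.923.

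**4. Gain.**

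| Contrast | Continuous | Planned GLM test | Gain | Fisher | Gain |
|---|---|---|---|---|---|
| H3a | 0.935 to 0.968 | 0.848 to 0.873 | 6 to 12 points | 0.822 | 11 to 15 points |
| H3b | 0.923 to 0.962 | 0.833 to 0.866 | 6 to 13 points | 0.815 | 11 to 15 points |

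**5. If atrophy means positivity on either signature.** The 19.3% is a prevalence of atrophy of either kind, so it may combine two measures. Assume two equally affected normal signatures with correlation 0 to 0.7, both assumptions of this check. Choose the cut so that 19.3% are positive on at least one, and the shift so that 48.25% are. The difference per signature is then d = 0.69 to 0.78. H3a power per signature is 0.89 to 0.95 at alpha 0.05, and 0.83 to 0.92 at alpha 0.025 if alpha is split. Against 0.85 to 0.87, the split-alpha change runs from about −4 to +7 points.

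**6. The planned predictor.** In B.2.3 the H3a predictor is repeated GCP, not delirium. A simulation with one continuous GCP slope and n = 126 shows a loss of about 15 to 17 points where binary power is near 0.82 (correlation about 0.35). At a correlation of 0.25 the loss is about 26 to 32 points. The protocol states no such correlation, so these values only illustrate direction.

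**The case against.** The strongest reply is that the protocol never says the binary variable is a cut of one thickness-change score. The reference prevalence covers either of two kinds of atrophy, so a classification on two signatures is a fair reading. A continuous analysis would then need two outcomes, and step 5 shows that the gain may disappear if each is tested at half the alpha. This stands, and it limits the size of the point.

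Several further objections also stand:
- The planned GLM tests are more powerful than Fisher's test, so a flat loss of 15 points, which a reader might infer by comparing 0.97 with 0.82, is only the top of the range.
- The 0.82 belongs to a delirium contrast that the H3a model in B.2.3 does not test.
- In the Aim 1 and 2 models, thickness is a predictor rather than an outcome, and its SD is cross-sectional. Those aims show that the continuous measure exists, not how variable its one-year change is.

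It may also be said that an SAP could supply the cut-point or a continuous sensitivity analysis. A missing cut-point alone would indeed be no finding. The binary outcome, however, is not left open: the protocol chooses it for both analysis and power, and naming a cut-point later would not recover what the split discards.

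**Conclusion.** The point holds as one of avoidable inefficiency. The protocol commits to a binary outcome, without a reason, for something measured by paired MRI in a sample that cannot grow. If atrophy is a cut of one roughly normal change score with equal SDs, continuous analysis of the H3a delirium contrast has power of about 0.94 to 0.97. The gain is 6 to 12 points over the planned GLM test and 11 to 15 over the stated figure. It is smaller, and possibly nil, for two signatures tested separately at a split alpha. For the model with GCP as predictor it is an analogy.

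Two stronger readings are not supported. The stated powers are not wrong: both reproduce and exceed 0.80. Nor is the log link at fault: the loss comes from the split, and the link supplies the relative risk on which the aim was powered.

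**What to change.** In B.2.3, Project 3, Aim 3, make the continuous one-year change in signature thickness the primary outcome, in an identity-link linear model adjusted for baseline thickness and the planned covariates. State how the AD and aging signatures are handled, by a composite or by a multiplicity adjustment. Keep the binary log-link model as a secondary analysis, with its atrophy criterion defined, so that relative risks remain available.

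In B.1.3, Project 3, Aim 3, give power for the continuous outcome in standardized units and state the assumption behind it. Power in mm cannot be derived from the protocol, which gives no SD for one-year change.

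The cost is revised wording and a rerun of the power text; no new data are needed. The downside is that primary results become mm differences rather than relative risks, and two signatures need a combined or adjusted test.

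### Project 3 Aim 3 enters GCP visit by visit as predictors of one-year atrophy, so no single parameter measures decline or answers H3a

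*Protocol*

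**What the plan says.** Section B.2.3 (Project 3, Aim 3) sets the direction of the model: "We will treat atrophy as a binary outcome variable in the multivariable GLM model with log link". The predictors are "repeated GCP measurements as independent variables. We will estimate the slope of GCP at each follow-up time point". A remedy for collinearity follows, on a condition: "In the event that we have high correlation among the GCP measurements, we will make use of the distributed lag model". For H3b the model gains delirium status and "the interaction between GCP and delirium status, and will obtain GCP slope conditioning on delirium status".

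Section A.2.3 says when atrophy is determined: "measured preoperatively and one year after surgery". The data are from SAGES I, "n=126 with longitudinal MRI". Section B.1.3 (Project 3, Aim 3) gives the group sizes: "Of the 126 subjects, 22% (n=28) subjects had delirium, and 98 did not". It assumes atrophy in 19.3% of patients without delirium and a relative risk of 2.5, and states power of 0.82 for H3a.

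Elsewhere the protocol treats decline as one quantity. Section B.1.3 (Project 1, Aim 2) reduces it to one time slope per patient. Section B.2.3 (Project 1, Aim 1) models GCP as a repeated outcome over three periods and tests an interaction with the period after two months. In Project 3 Aim 1, H1b also has longitudinal GCP as the dependent variable.

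**The concern.** Aim 3 asks whether atrophy goes with long-term cognitive decline. The model does not contain a decline. It contains a set of GCP levels, and the coefficient for one level with the others held fixed mixes level, change and measurement error. A reader given one coefficient per visit cannot tell which of them, or which combination, answers H3a.

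Two features add to this. First, Section A.2.4 describes SAGES I decline out to 36 months and defines complicated delirium by decline over two to three years or more. Much of the information on long-term decline therefore comes after the one-year MRI at which the outcome is fixed. Second, the sample is fixed and small, and repeated scores on one patient are strongly correlated. Spreading one question over several collinear terms costs power if they are tested together, and costs error control if they are read one by one.

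**Working it through.** **1. The plan's own figure.** Inputs from Section B.1.3: 28 patients with delirium and 98 without; atrophy 0.193 without delirium and 2.5 x 0.193 = 0.4825 with it; two-sided 0.05. Exact power of Fisher's test is 0.822 (stated 0.82). For H3b, with 20 against 78 patients and 2.75 x 0.193 = 0.531, it is 0.815 (stated 0.81). Both figures reproduce. They compare atrophy prevalence between groups defined by delirium, or by delirium plus decline. Neither concerns a model with GCP terms.

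**2. Events per term.** Expected atrophy events: 98 x 0.193 + 28 x 0.4825 = 18.9 + 13.5 = 32.4, or 25.7% of 126. The visit months for SAGES I are not in the protocol. Assume the SAGES II schedule in Section A.2 (1, 2, 6, 12, 18, 24 and 36 months), which has seven visits, three of them after month 12. Then 32.4 / 7 = 4.6 events per GCP term. If H3b adds delirium and seven interactions there are 15 terms, and 32.4 / 15 = 2.2. Both counts are before confounders.

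**3. Reading terms singly.** If the terms were independent and each tested at 0.05, the chance of at least one false positive is 1 - 0.95^7 = 0.302 for seven visits and 1 - 0.95^3 = 0.143 for three.

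**4. Simulation.** The protocol gives no GCP variances, so these are assumptions. GCP at visit j is a_i + s_i t_j + e_ij, with SD(a) = 1, SD(s) = 0.15 or 0.30 per year and SD(e) = 0.3 or 0.5. The logit of atrophy is c - b x s_i / SD(s), with c set for 25.7% prevalence. There were 126 patients per sample and 2,000 samples per setting. The tests were one least-squares slope per patient over months 2 to 36 (1 df), a distributed lag with coefficients linear in time (2 df, constraint assumed), all seven visit terms jointly (7 df), and any single visit term at 0.05.

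| SD(e) | SD(s) | b | one slope | linear lag | 7-df joint | any of 7 |
|---|---|---|---|---|---|---|
| 0.3 | 0.15 | 0 | 0.062 | 0.060 | 0.077 | 0.296 |
| 0.3 | 0.15 | 0.6 | 0.586 | 0.515 | 0.336 | – |
| 0.3 | 0.15 | 0.8 | 0.769 | 0.728 | 0.550 | – |
| 0.5 | 0.15 | 0 | 0.060 | 0.061 | 0.074 | 0.307 |
| 0.5 | 0.15 | 0.6 | 0.379 | 0.341 | 0.212 | – |
| 0.5 | 0.15 | 0.8 | 0.548 | 0.513 | 0.341 | – |
| 0.3 | 0.30 | 0 | 0.056 | 0.060 | 0.075 | 0.292 |
| 0.3 | 0.30 | 0.6 | 0.740 | 0.668 | 0.473 | – |
| 0.3 | 0.30 | 0.8 | 0.917 | 0.879 | 0.717 | – |

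The any-of-7 column is left blank where b is above 0, because a rule with about 30% type I error has no comparable power.

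- *7-df joint test against one slope:* the loss runs from 0.379 - 0.212 = 17 points to 0.740 - 0.473 = 27 points. A separate run of 1,500 samples with baseline GCP also in the model gave 0.765 - 0.479 = 29 points, and 0.315 for any single term under no association.
- *Linear lag against one slope:* the loss runs from 0.548 - 0.513 = 3.5 points to 0.740 - 0.668 = 7 points. A quadratic constraint at b = 0.8 gave 0.679, 0.449 and 0.828 in the three variance settings, or 9 to 10 points below the slope. Type I error of the joint lag test was 0.05 to 0.06. Reading each lag singly still gave 0.10 to 0.15.
- *Link:* a log-link Poisson fit with robust standard errors (1,000 samples) showed the same pattern.
- *Visit schedule:* with visits only at 12, 24 and 36 months, one slope had power of 0.82 to 0.83 against 0.71 for the joint test, a loss of 11 to 12 points. Any-term false positives were 0.12 to 0.13.

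**The case against.** The strongest reply is that the protocol foresees the collinearity. In the simulations the mean correlation between visits was 0.79 to 0.90 and the largest variance inflation factor 5 to 14, so the stated condition for the distributed lag model would very likely be met. A low-order lag model gives back most of the power. This stands, and it limits the power argument to the unconstrained fit. It does not remove the structural problem: the lag model still reports an effect per time point and still uses scores taken after the outcome.

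A reader might infer that the plan carries a 30% false-positive rate. The protocol does not support that. It says the effects will be estimated; it does not say that each is tested at 0.05 or that one significant term counts as success. The rate is what would follow under such a rule.

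A reader might also infer that the test is invalid because later cognition is used to predict earlier atrophy. That goes too far. The aim is worded as an association, and an association can be tested from either side. Time order affects what the coefficients mean, not whether a test is valid.

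The seven-visit schedule belongs to SAGES II, and Section A.3 speaks only of annual testing for SAGES I. Fewer visits shrink the loss, as shown. The single slope is also favoured here because the data were generated with one linear slope per patient.

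Finally, Table 6 already lists repeated-measures and mixed-effects models for Project 3. It does not assign them to Aim 3, whose text specifies the other model.

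**Conclusion.** The point holds as a flaw in the choice of model, and the plan should be changed. The main Aim 3 analysis fixes a structure in which no one parameter is the rate of decline, whereas Project 1 and Project 3 H1b put GCP on the outcome side. This is a stated model, not detail left for an analysis plan.

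The size is conditional. On the assumed seven-visit schedule and variances, the unconstrained joint test loses about 17 to 29 power points against one slope, and single-term reading at 0.05 gives about 30% false positives. With three annual visits these fall to 11 to 12 points and 12 to 13%. Under the distributed lag fallback with an assumed low-order constraint, the joint test comes within about 10 points of the single slope. In every setting with a true effect, one slope had more power than the joint tests. The stated powers of 0.82 and 0.81 are correct for what they calculate but say nothing about this model.

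**What to change.** In Section B.2.3, Project 3 Aim 3, make repeated GCP the outcome in the piecewise mixed model already specified for Project 1 Aim 1. Name atrophy x long-term time as the single H3a test, and atrophy x delirium x long-term time as the H3b test.

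If atrophy is to stay the outcome, enter one long-term GCP slope per patient together with baseline GCP, and say how scores taken after the one-year MRI are used. Either way, keep visit-specific or distributed lag estimates as descriptive secondary output.

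The cost is a change of wording; no new data are needed, and mixed models are already listed for Project 3 in Table 6. Visit-specific coefficients would no longer be the main result. The change does not make H3b precise: only about 28 x 0.4825 = 13.5 atrophy events are expected among patients with delirium, so that interaction will be estimated loosely under any model.
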